Males VIGOROUS: Enter the number of vigorously active males in each of the four age categories. If there are no individuals in a given age group, leave the field blank.

Males Race/Ethnicity: Enter the number of males in each of the four race/ethnicity categories. If there are no individuals in a given group, leave the field blank.

Scan Complete: Check this box at the end of each target area scan. Tap the “End” tab after checking the box.

Survey/Entrevista

The English and Spanish versions of the survey are separate forms in Pendragon. Interviewers are required to enter the name of the park in which the interview is administered. Therefore, there will be a single Survey form and a single Entrevista form that will be used across all parks.

The full survey is available in the appendices. Highlighted here are some fields that will assist with data management.

Park user activity level: Choose either Active or Sedentary to indicate the level of activity of the park user survey respondent. This field is completed for park user surveys only.

Partial Survey: This check box is located on the final screen of the Survey/Entrevista form. Check this box if you begin a survey, but are unable to complete it for any reason (e.g., participant chooses to end it early). If you complete the full survey leave this box unchecked.

Full survey completed: Check this box if you administer the full survey, even if the participant chooses not to answer some of the questions. If you checked the Partial Survey box, do not check this box.

Environmental scan

This form is used to provide an overall impression of the park after each park scan is complete (e.g., 3x/day). Only one person from the team needs to enter the data, but team members should discuss the items as needed to come to an accurate assessment.

Observers are required to enter the name of the park being assessed. Therefore, there will be a single Environmental scan form that will be used across all parks.

The environmental scan form contains the following data fields.

Date and Time: Check to ensure that the proper date and time are displayed.

Park name: Choose the appropriate park from the lookup list.

Your name: Choose your name from the lookup list.

Weather: Mark ‘Yes’ or ‘No’ for each of the four items listed below:

- Windy
- Pleasant
- Too cold
- Too hot

Safety: Mark ‘Yes’ or ‘No’ for each of the four items listed below:

- Conflict (fight)
- Gang members

- Stray dogs
- Intoxicated people

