Appendix C: Park user and household survey (English)

Revised 6/11/13

NEIGHBORHOOD PARKS

Interviewer: _____ Date: _____ Time: _____ AM / PM (Circle one)

Participant type: Park user ¼ mile resident ½ mile resident 1 mile resident
 Station ¼ mile Station ½ mile Station 1 mile

Gender: Male Female Age: _____ Activity level: Sedentary Active

INTERVIEWER TO READ STATEMENT: This survey is mainly about _____ [park name]. Please think about this park when you answer the questions.

1. How many children under the age of 18 do you have?

_____ (insert number)

2. How do you describe yourself in terms of race or ethnicity? (Check one)

- Latino Asian / Pacific Islander
- White American Indian / Alaska Native
- Black Other _____

3. How often do you come to this park? (Check one)

- Daily
- A few times a week
- Once per week
- A couple times per month
- Monthly
- A few times a year
- This is the first time
- Never [skip to #10]

4. How many times did you visit this park within the past SEVEN days?

_____ (insert number)

- Don't know

5. On a typical day when you go to the park, how long do you stay there?

(Check one)

- 0-30 minutes 2 – 3 hours
- 31-60 minutes > 3 hours
- > 1 hour, but < 2 hours

6. When was the first time you came to this park?

(Check one)

- Today
- This month
- In the past 6 months
- Between 6 - 11 months ago
- Between 1 - 2 years ago
- More than 2 years ago

7. How do you usually get to the park?

(Check one)

- Walk
- Bike
- Car
- Bus or other public transportation
- Other _____

8. What do you usually do while at this park?

(Check all that apply)

- Aerobics Meet friends
- Baseball/softball Playground
- Basketball (indoors) Sitting in park
- Basketball (outdoors) Skating
- Celebrations or picnics Soccer
- Classes Swimming
- Frisbee Tennis
- Gymnasium activity Volleyball
- Gymnastics equipment Walking
- Handball Walking with dog
- Other _____

9. When you are at this park, do you run into people you know? (Check one)

- Yes, often Rarely
- Yes, sometimes No, not at all

10. If you do not visit this park, why not?
(Only ask this question if the respondent answered "Never" to question 3)

11. How would you grade the park staff with respect to their helpfulness, friendliness, and professionalism?
(Check one)

A D
 B F
 C Don't know the staff

12. In general, how safe do you feel the park is?
(Check one)

Very safe
 Safe
 Not very safe
 Not safe at all

13. Where do you usually exercise? *(Check one)*

I don't usually exercise
 Park
 Home

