5. There are no special instructions related to the race/ethnicity of participants. However, note that in some parks you should expect to interview more individuals of certain race/ethnicity groups.
 - a. Poinsettia RC and Hoover RC, expect to interview more White participants.
 - b. St. Andrews RC, Van Ness RC, Jim Gilliam RC, expect to interview more Black participants.
 - c. Alpine RC and Seoul International RC, expect to interview more Asian participants.
 - d. In all other places, expect to interview a majority of Latino participants.

Administration

On each survey there are two required fields to help track adherence to the quota design: 1) Gender, and 2) Activity level. These fields must be completed before proceeding to the rest of the survey questions.

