We used negative binomial distributions in the DID models due to the sizable heteroscedasticity in park use outcomes (Cohen et al., 2012). Effects of the intervention were presented in the scale of multiplicative scale (i.e., % changes) in these models. We also examined the outcomes by two age groups (youths versus adults). In analyzing survey outcomes, we controlled for respondent-level covariates to reduce estimation biases because randomization was not at the individual level, including gender, age, education level, obesity status, address buffer (<.25 mile, .25 to .5 miles, and .5 miles to 1 mile to park), self-rated health, perception of park safety, primary language, and having children under 18 years old. All statistical models were fitted in SAS 9.4. We also conducted sensitivity analyses using robust standard errors for park clustering effects and alternative scale for transformed mean outcomes (log or logit) wherever appropriate. The main findings were not sensitive to alternative model specifications.

Statistical power: This study was powered to detect a small to medium standard effect size under the regular setting of two-sided p -value <0.05 and power >0.80 . With 12 parks in each study arm and the extensive repeated measurements in each park (18 hourly observation per wave for two waves), we can detect a difference of 0.34 times standard deviation (SD) between any two arms when the intra-class correlation is no greater than 0.10. Based on historic data from previous studies (average park use 55 persons/hour, $SD=35$, approximately)(Cohen et al., 2013) meant that we could detect an additional 11.9 persons/hour. Because most survey outcomes were categorical, we used a two-sample z -test for calculating the detectable effect size for survey analysis. With 20 surveys in each wave and in each park's neighborhood, we could detect a difference of 15 percentage points for a binary outcome with a baseline prevalence between 20% and 80%. The detectable effect size is even smaller if the baseline prevalence rate is very high or very low (e.g. $<20\%$, or $>80\%$).

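### The survey models adjust for nine respondent characteristics but not for race/ethnicity, which item 2 collects, and the undefined language covariate cannot stand in for it

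*SAP*

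**What the plan says.** The SAP (Data analyses) explains the adjustment of the survey outcomes this way: "we controlled for respondent-level covariates to reduce estimation biases because randomization was not at the individual level". The covariates follow: "including gender, age, education level, obesity status, address buffer", then self-rated health and perceived park safety, and finally "primary language, and having children under 18 years old". That makes nine, and race/ethnicity is not among them.

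The Protocol uses one instrument for park users, residents and station respondents (Data Collection). Item 2 asks: "How do you describe yourself in terms of race or ethnicity" (Appendix C, with a Spanish counterpart in Appendix D). On language, the Survey/Entrevista section says: "The English and Spanish versions of the survey are separate forms in Pendragon". The Data export section gives the two forms separate file names.

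The park-user recruitment guide warns interviewers that "in some parks you should expect to interview more individuals of certain race/ethnicity groups" (Appendix F, Selecting Participants). It then names seven parks where more White, Black or Asian participants are expected, and expects a Latino majority elsewhere.

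**The concern.** The SAP's reason for adjusting is that individuals were not randomised, so the people interviewed may differ in ways that randomisation of parks does not balance. That reason applies to race/ethnicity as directly as to education or language. The study records race/ethnicity throughout its other instruments: the second park counter, the park, path and Fitness Zone scans, and the interview log.

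A reader may assume that the language covariate covers the gap. It does not, because its source is undefined and the only available source is coarse. If the racial/ethnic mix of respondents moved between waves in one arm and not in another, part of that movement would be read as a wave-by-arm effect on the survey outcomes: park visits, duration of visits, awareness of and participation in programs, perceived park safety, and exercise sessions.

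**Working it through.** **Step 1. Compare the covariate list with the instrument.** I set the nine SAP covariates against the survey header and items 1 to 45 in both language versions.

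- Race/ethnicity: collected by item 2, absent from the SAP list.
- Primary language: no header field or item asks it. The only trace is which Pendragon form, and so which export file, holds the interview.

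**Step 2. Ask what form language can distinguish.** It has two values. All Spanish interviews share one. Black, White, Asian and Latino respondents interviewed in English share the other. As a measure of primary language it also misclassifies bilingual respondents and speakers of a third language.

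**Step 3. Ask when the omission biases the estimate.** The effect is the wave-by-arm interaction in a model with park random effects (SAP, Data analyses). The same parks are measured in both waves, so composition that stays constant within a park largely drops out. For one group against the rest, approximately:

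bias = (outcome gap between groups) × (between-arm difference in the wave-to-wave change in group share).

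The documents give neither factor. As an illustration only, an assumed gap of 20 points and an assumed differential shift of 10 points give 0.20 × 0.10 = 0.02, or 2 points. The SAP's stated detectable difference is 15 points.

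**Step 4. Ask whether a differential shift is possible.** Interviews carry no personal identifiers (Appendix K), and nothing links respondents across waves. Invalid or vacant addresses and refusals lead to replacement addresses (Appendix G). Where residents cannot be reached at home, a convenience sample at stations or storefronts is used instead (Data Collection). The share of such substitutions could differ by wave and arm. No passage says that it does.

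**Step 5. Size of the precision gain.** Inputs: 12 parks per arm and 20 surveys per park and wave (SAP, Statistical power), so n = 12 × 20 = 240 per arm and wave. Assumed: 50% prevalence, a group share of 40%, gaps of 10 to 30 points, independent respondents.

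- Unclustered standard error of the effect: √(4 × 0.25 / 240) = 0.0645, about 6.5 points.
- Chance SD of the between-arm change in share: √(4 × 0.24 / 240) = 0.063, or 6.3 points.
- Contribution to the estimate: 0.063 × 0.10 = 0.6 points, to 0.063 × 0.30 = 1.9 points.
- Fraction of variance removed: gap² × 0.24 / 0.25, which is 0.0096 at a gap of 0.10 and 0.0864 at 0.30. The sample size cancels.
- Reduction in standard error: 1 − √(1 − 0.0096) = 0.5%, to 1 − √(1 − 0.0864) = 4.4%.

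If groups concentrate by park, the within-park variance is below 0.24. An assumed 0.10 gives a chance SD of √(4 × 0.10 / 240) = 4.1 points, and smaller gains. Clustering of the outcome also lowers the relative gain.

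**The case against.** Four objections carry weight.

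First, Appendix F concerns park-user interviews, while the SAP speaks of resident survey respondents and of surveys in each park's neighborhood. It also describes differences between parks, not between arms or over time. A reader might infer from it that the arms are confounded by race/ethnicity. The documents do not support that: parks were randomised, and stable composition largely cancels in the model. This stands. Appendix F shows that the variable varies in this setting, and nothing more.

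Second, a reader might infer that the language covariate has no data behind it. That is too strong, because the form used records interview language. The instrument shown is also a single version, marked as revised in June 2013; a different second-wave version, if there was one, is not in the documents. What remains is a missing definition and a mislabelled variable.

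Third, chance imbalance in mix is already inside the standard error, so the 0.6 to 1.9 points are not an extra error. This stands, which is why Step 5 expresses them as a precision gain.

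Fourth, the list opens with a word that may mean it is not exhaustive, and covariates already in the model, such as education and interview language, may absorb part of any shift. Both are possible. If race/ethnicity was in the models, the SAP should say so. The reported sensitivity analyses vary the standard errors and the outcome scale; none is described as varying the covariates.

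**Conclusion.** The point holds as a modest gap in the survey analysis. A collected variable that fits the SAP's own reason for adjustment is left out without explanation, and interview language cannot replace it.

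Bias is possible but not shown. It needs a change in respondent mix that differs by arm, and the documents give no figure for one. The 2-point illustration is the product of two assumed values and should not be read as an estimate. The precision gain is about 0.5% to 4% under the assumptions in Step 5, and less with clustering or with groups concentrated by park.

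Only the survey outcomes are touched. Energy expenditure and the number of observed park users come from SOPARC observation and do not depend on these covariates.

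**What to change.** Add item 2 race/ethnicity to every survey-outcome model. Collapse sparse categories, for example to Latino, Black, White, Asian/Pacific Islander and other, and add a category for missing answers, since the Protocol allows skipped questions and partial surveys. Report the survey estimates with and without it. Because the SAP describes models already fitted, present the comparison as a sensitivity result, not as pre-specified.

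Relabel the language covariate as interview language (English or Spanish form) and state that it comes from the form used.

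The item is already in the instrument. Five collapsed groups use four degrees of freedom and a missing category one more. The new covariate will overlap in part with interview language, so the two coefficients should not be interpreted separately; the intervention estimate is what matters.

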While routine physical activity is critical to optimal health, our preliminary studies have indicated that residents of low-income communities in Los Angeles are less likely to exercise than those in high-income communities, and they are less likely to use their neighborhood parks, even when the parks are within walking distance. Parks in low-income neighborhoods tend to be smaller and serve a greater population density, but even after accounting for the size and the population served, they are still used less than parks in wealthier neighborhoods. In our preliminary studies, we found that parks in low-income neighborhoods also had fewer part-time staff and offered fewer programs and organized activities than parks in higher-income areas, and these factors partly accounted for their lower use. As well, parks in low-income neighborhoods are often perceived as less safe, a characteristic associated with lower use. Simultaneously, the lack of use and dearth of programming may contribute to a perception of lack of safety, creating a vicious cycle. Nonetheless, we have documented that when parks in low-income neighborhoods offer events and activities, they can be just as busy as parks in higher-income areas. We hypothesize that limited park use in low-income areas can be attributed to the lack of organized and reliable infrastructure of activities that meet the needs of local residents and that offering more activities and programs in parks will increase park use and park-based physical activity.

According to the Task Force on Community Level Preventive Services, community-level campaigns are both effective and scalable. For the past eight years, we have conducted research in public neighborhood parks and found that these venues offer great potential for increasing physical activity for populations. Based upon this work, as well as our previous work on the cost-effectiveness of physical activity interventions, we propose to test community-level campaigns targeting low-income populations that will be relatively low-cost and easy to replicate.

The study has three specific aims:

1. Using a full factorial design, compare whether park use and population physical activity in low-income neighborhoods increase with the availability of a) more organized physical activity classes, including Zumba, line dancing, and aerobics indoors and outdoors, and/or b) a loyalty program approach that rewards frequent park users.

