Appendix G: Household interview recruitment guide

Household Sample

Interviewers will survey residents living at designated addresses within one quarter (1/4 mile), one half (1/2 mile), and one (1 mile), of the park. RAND will identify residential addresses within each of these three different distance areas and provide them to Interviewers by the first day of each park observation. The goal is to interview members of 10 households in each stratum, or complete 30 interviews.

The Interviewer (you) will need to determine if those addresses are appropriate for including in the study. In some cases, multiple residences may be associated with a single address (e.g. apartment buildings) or the address may not be valid (e.g., commercial buildings, vacant lots, condemned home). You must follow the established protocols to ensure that the interviewing methods meet scientific research criteria.

Selecting Apartments

When the provided address is to an apartment building, individual units are determined as follows:

1. The **1st time** you encounter this scenario, take the stairs to the **second floor** of the building. Approach the **first apartment to the right**. This protocol should be followed for all oddly numbered subsequent occurrences (3rd time, 5th time, 7th time, etc.). [If the apartment building is a single story, follow the directions in #2.]
 - a. On the Household Interview Log, enter the apartment number next to the printed address AND note that the apartment is on the second floor.
2. The **2nd time** you encounter this scenario, select the **first apartment to the right** on the **first floor** of the building. This protocol should be followed for all evenly numbered subsequent occurrences (2nd time, 4th time, 6th time, etc.).
 - a. On the Household Interview Log, enter apartment number next to the printed address AND note that the apartment is on the first floor.

Selecting Freestanding Units

When there is more than one freestanding unit at the provided address, determine which unit to approach as follows:

1. The **1st time** you encounter this scenario, select the **first unit** you approach when walking onto the property. This protocol should be followed for all oddly numbered subsequent occurrences (3rd time, 5th time, 7th time, etc.).
 - a. On the Household Interview Log, enter the unit number (e.g., Unit A or front house) next to the printed address.

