Promoting Physical Activity in High Poverty Neighborhoods

NCT # NCT01925404

September 26, 2017

Data analyses

We first conducted descriptive analyses of park characteristics, park baseline observation data, and characteristics of resident survey respondents. To obtain community level population data we used census data and GIS methods to calculate population density and socio-demographic characteristics of the population within a one-mile radius of each park (USCensus, 2010a, 2010b). We calculated the violent crime rate in the park neighborhoods (1-mile radius around the study parks) using a City of Los Angeles Police Department publicly available dataset (DataLA, 2016). We also summarized process measures for the intervention by study arms. We then conducted formal statistical analyses of park use outcomes and survey data. The primary pre-specified outcome was estimated energy expenditure in parks from the SOPARC observations using MET scores, the ratio of work metabolic rate to standard resting metabolic rate. We assigned MET levels of 1.5 for sedentary, 3 for moderate, and 6 for vigorous activity as identified by Ainsworth et al (Ainsworth et al., 2000). The secondary outcome measure was the number of observed park users. Survey outcomes included self-reported park use (number of visits in past seven days, duration of park visits, awareness of park programs, having participated in park programs), perception of park safety, and number of weekly exercise sessions.

We fitted difference-in-differences (DID) models between the two measurement waves and four study arms (Yang & Tsiatis, 2001). The effect of the intervention was modeled as the wave by study arm interaction. All models used random effects to account for intra-class correlation within each park as well as fixed effects to account for observation times (time of day, weekend versus weekdays). This approach can eliminate temporal trends unrelated to the intervention and is particularly suitable for this study due to the relatively long observation periods. We also included indicators for park cohorts to account for potential seasonal effects.

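### The 15-point detectable difference for survey outcomes comes from a two-sample z-test; a pairwise difference-in-differences on the same surveys needs about 18 points at 50% prevalence

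*SAP*

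**What the plan says.** The SAP sets its power requirement at "two-sided p -value <0.05 and power >0.80". For the surveys, the Statistical power paragraph says a two-sample z-test was used for "calculating the detectable effect size for survey analysis". The result is: "With 20 surveys in each wave and in each park's neighborhood, we could detect a difference of 15 percentage points for a binary outcome", for baseline prevalence between 20% and 80%. No arm contrast, intra-class correlation (ICC) or design effect is given for this calculation. The number of parks comes from the preceding sentence on the observation outcome: "With 12 parks in each study arm and the extensive repeated measurements in each park". That sentence refers to a comparison of any two arms.

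The Data analyses section announces formal analyses of both park-use outcomes and survey data. It then describes DID models over two waves and four arms: "The effect of the intervention was modeled as the wave by study arm interaction". It continues: "All models used random effects to account for intra-class correlation within each park". It gives no other definition of the effect for survey outcomes.

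Two places in the Protocol bear on the point. Specific aim 1 begins "Using a full factorial design, compare whether park use and population physical activity in low-income neighborhoods increase", and Appendix G sets the household target per park: "The goal is to interview members of 10 households in each stratum, or complete 30 interviews".

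**The concern.** A two-sample z-test compares two independent proportions. A wave-by-arm interaction between two arms is a difference of two differences, so it carries the sampling variance of four proportions. When each wave samples its own respondents, the variance about doubles and the detectable difference grows by about the square root of 2. A figure computed for the simpler comparison therefore overstates the sensitivity of the planned one, unless it already holds enough reserve.

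What is at stake is how a null survey result is read. Perceived park safety is a survey outcome and the subject of Aim 2. If no change is found, a reader may conclude that a 15-point effect was excluded with at least 80% power. Over most of the stated prevalence range, the pairwise contrast does not support that conclusion.

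**Working it through.** **Inputs.** From the SAP: two-sided 5% and 80% power, so k = 1.960 + 0.842 = 2.802; 12 parks per arm; 20 surveys per park per wave. This gives n = 12 × 20 = 240 per arm and wave. Respondents are treated as separately sampled in each wave. Let p be the baseline prevalence and d the effect.

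**1. The SAP's own method.** Two-sample z-test, 240 against 240, p = 0.5:
- Equal variances: d = 2.802 × √(2 × 0.25/240) = 0.128.
- Unequal variances, solving d = 2.802 × √{[p(1−p) + (p+d)(1−p−d)]/240}: d = 0.126.
- Power for 15 points: about 92%.

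The stated inputs give 12.6 to 12.8 points, so 15 contains a reserve that the SAP does not explain. As a variance factor the reserve is (0.15/0.128)² = 1.38, or 1.44 with unequal variances. A design effect of 1.38 would produce it (with 20 per park, an ICC of about 0.02). So, roughly, would 90% power or a Bonferroni correction for three comparisons (14.8 points each).

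**2. Pairwise DID, no clustering.** Three cells are at p and one at p + d:

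d = 2.802 × √{[3p(1−p) + (p+d)(1−p−d)]/240}

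| Baseline prevalence | Points needed (increase) | Power for 15 points |
|---|---|---|
| 20% | 15.2 | 79% |
| 30% | 17.0 | 70% |
| 40% | 17.8 | 66% |
| 50% | 17.8 | 65% |
| 60% | 17.1 | 68% |
| 70% | 15.7 | 76% |
| 75% | 14.6 | 82% |
| 80% | 13.3 | 89% |

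The need equals 15 points at p = 0.734. For a decrease the table is mirrored about 50%. With all four cells given the same variance at 50%, d = 2.802 × √(1/240) = 0.181.

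The power at 50% follows from SE = √(0.9775/240) = 0.0638: Φ(0.15/0.0638 − 1.96) = 0.65. A simulation of 40,000 trials gave SE 0.0641 and power 0.648.

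**3. Does the reserve cover it?** The ratio of DID variance to z-test variance is 2.00 with equal cells and 0.9775/0.4775 = 2.05 with unequal cells. The reserve is 1.38 to 1.44, so it does not.

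**4. Clustering.** The documents give no survey ICC, so these values are assumptions.
- A park effect that is constant over both waves cancels in the DID. At a constant ICC of 0.10 the simulated SE is 0.0608, so the need is 2.802 × 0.0608 = about 17.0 points.
- Park-by-wave variation does not cancel. With a design effect of 1 + 19 × ICC, the need at 50% is 19.4 points at ICC 0.01, 20.8 at 0.02 and 24.5 at 0.05.

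**5. Other contrasts and counts, at 50%.**
- Factorial main effect by DID (24 against 24 parks, 480 per cell, no interaction): 12.7 points, or 14.9 at an assumed park-by-wave ICC of 0.02.
- Pairwise DID with 30 surveys per park per wave (360 per cell): 14.6 to 14.8 points with no clustering, and 16.5 at an assumed park-by-wave ICC of 0.01.

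**The case against.** The strongest reply is that the pairwise survey contrast is inferred. The comparison of any two arms belongs to the sentence on the observation outcome, and the survey sentences name no contrast. The design is factorial, and Aim 2 asks about each of the two approaches, which a main effect can answer. A main-effect DID has variance 4p(1−p)/480, identical to the z-test's 2p(1−p)/240. On that reading nothing is lost, and a design effect of 1.38 brings the figure to about 15. This stands as a limit: the shortfall belongs to the pairwise contrast. It does not rescue the text, because the SAP models four arms and nowhere states a main-effect contrast or the no-interaction assumption.

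It can also be said that the DID description may not extend to the surveys, since the same paragraph lists observation-schedule terms such as time of day. Yet survey data are announced just before it, surveys were taken in each wave, and no other effect is defined. The reading is from context, but it is the natural one.

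Three mitigations hold in part. The gap is small at the edges of the range: 14.5 points at 20% and 80% with equal cell variances. Reaching 30 household interviews in each wave would close it if there were no park-by-wave variation, but the SAP's claim rests on 20. Covariate adjustment might gain precision, but the documents do not quantify this.

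Finally, the SAP reports completed analyses, and confidence intervals will inform a null result better than a planning figure. That limits the consequence; it does not make the stated figure right.

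**Conclusion.** The concern holds for the pairwise contrast. At 50% prevalence with 20 surveys per park per wave, the DID between two arms needs 17.8 to 18.1 points against the stated 15, and 15 points has about 65% power against the required 80%. For an increase, the claim fails from 20% (narrowly) to about 73% prevalence and is met above that.

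This rests on three assumptions: that the survey effect is the wave-by-arm interaction, that each wave has separate respondents, and that there is no park-by-wave variation. Any such variation widens the gap; a constant park effect narrows it slightly. Under a factorial main effect without interaction there is no shortfall when clustering is ignored. The primary and secondary outcomes, the sample size and the models are unaffected. The point should be corrected because it governs how null survey findings are interpreted.

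**What to change.** Reword the survey part of the Statistical power paragraph:

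- Name the contrast analysed for survey outcomes and compute the detectable difference for it.
- If it is pairwise, state about 18 points at mid-range prevalence with no park-by-wave variation. Add that the need for an increase is about 15 points at 20% and below 15 from about 73% upward.
- If it is a factorial main effect, say so, state the no-interaction assumption, and give about 12.7 points at 50%.
- Apply any design effect, 1 + (m − 1) × ICC with m surveys per park per wave, to the park-by-wave component only, and label the ICC as an assumption (for example, about 21 points pairwise at 0.02).
- Explain what reserve the 15 points contained, and whether 20 surveys was a deliberately cautious input beside the 30 household interviews in Protocol Appendix G.

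The cost is one rewritten paragraph and, for the pairwise contrast, a less favourable figure. No surveys are added and no model changes.
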